7.2.2. Planned CV Safety (MACE) Co-Primary Statistical Analyses

CV Safety (MACE) Co-Primary Statistical Analyses
Endpoint(s)

 • Time to first occurrence of adjudicated MACE • The Cox Proportional Hazards model will adjust for the following baseline categorical values: 
 ○ Treatment ○ Current ESA use (as randomized, see Section 10.10.2) ○ Region (as randomized, see Section 10.9 & Section 10.10.2) • Confidence intervals for the rate per 100 person-years will also be reported. For within-group rates, the two-sided 95% CI will be obtained using an exact Poisson method. For difference in rates between treatments, the two-sided 95% CI will be constructed with a Normal approximation using Wald’s method [Liu, 2006]. • The co-primary analysis will use only adjudicated safety endpoints as determined by the clinical endpoint committee (CEC) within the time period for follow-up of CV endpoints defined in Section 10.6.4. • Calculation of time-to-event or censoring is described in further detail in Section 10.6.4. • First occurrence of adjudicated MACE for a subject is defined as the first adjudicated event, determined by the event date, that is indicated as all-cause mortality, non-fatal MI or non-fatal stroke with further details in Section 10.6.4.
Model Checking & Diagnostics

 • Refer to Appendix 12: Model Checking and Diagnostics for Statistical Analyses.
Model Results Presentation

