
 • In addition to the baseline categorical values (i.e. Treatment, Current ESA use, Region) that will be adjusted in the co-primary MACE analysis, additional covariates will be included in the Cox Proportional Hazards model: 
 ○ Continuous variables: baseline Hgb, baseline Age, baseline eGFR, logarithm of baseline UACR, baseline albumin ○ Binary variables: sex, history of myocardial infarction, history of stroke, history of heart failure, history of atrial fibrillation, history of diabetes ○ Non-binary categorical variable: race (Asian, Black, White, Other) • For a continuous variable, missing values will be imputed using the mean of all observed values of that variable in the overall study. For a binary variable, missing values will be imputed

Supportive Statistical Analyses

using a Bernoulli distribution with probability as the observed percentage of “Yes” (or “Female”) in the overall study. For race, missing values will be imputed as “Other”.

- This analysis will use the time to the first occurrence adjudicated MACE endpoint, and will use the time period for follow-up of CV endpoints as described in Section 10.6.4.
- The HR, associated two-sided 95% CI and one-sided non-inferiority and superiority p-values from this supportive analysis will be included on a forest plot with the co-primary MACE results.

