
 CKD progression is defined as (see Section 10.6.4): 
 40% decline in eGFR from baseline (confirmed 4 – 13 weeks later) or; End stage renal disease (ESRD) as defined by either: 
 Initiating chronic dialysis for ≥ 90 days*, or Not initiating chronic dialysis when dialysis is indicated (adjudicated), or Kidney transplantation 
*Adjudicate only if the duration of dialysis is <90 days.
 For purposes of summary and analysis, the components of CKD progression include: 
 Confirmed 40% eGFR decline Chronic dialysis. The chronic dialysis component includes subjects who initiate chronic dialysis for ≥ 90 days (non-adjudicated), positively adjudicated cases of dialysis less than 90 days with expected chronicity, and positively adjudicated cases where dialysis was indicated for a chronic condition but not provided. Kidney transplant Summaries and Analysis of CKD progression and its components will be restricted to the subset of subjects with baseline eGFR ≥ 15 ml/min/1.73m². Due to the presence of all-cause mortality as a competing risk, analysis of time to progression of CKD will be performed using Fine and Gray's subdistribution hazards analysis model, adjusting for the same factors as the co-primary MACE analysis (Section 7.2.2) for the evaluation of superiority. 
 For supportive purposes, the Cox Proportional Hazards model used in the co-primary MACE analysis will also be run. Analysis will include only the CKD progression events occurring within the time period for follow-up of CV endpoints as described in Section 10.6.4. For the components of CKD progression intended to go through the adjudication process, only the adjudicated results will be used.
Model Results Presentation

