
 ● The difference in change from baseline in eGFR at Week 52 will be analyzed with a mixed model repeated measures (MMRM) approach with an unstructured covariance matrix to compare the difference in means between arms. The models will be fitted to scheduled eGFR data collected after baseline up to Week 52. The models will include treatment, time, prognostic randomization stratification factors (see Section 10.10.2), baseline eGFR, baseline eGFR by time, and treatment by time interaction terms. Analyses will be done with the MIXED procedure in SAS, using the Kenward-Roger option to estimate denominator degrees of freedom and standard errors. ● For the summary table of rate of decline, each subject's actual time since randomization will be used, rather than assigning visit as a categorical variable. For each individual subject in the ITT Population, eGFR will be regressed on time (as a continuous variable), to estimate a slope for each subject. The baseline value of eGFR will be the first value used in the regression. The individual regression slopes will be expressed in ml/min/1.72m² per year. ● For the analysis of rate of decline, the mean slope for eGFR during the study will be estimated by a linear mixed model with random intercept and time to account for between-subject variability. The models will be fitted to scheduled eGFR data collected after baseline, and will include treatment, time, prognostic randomization stratification factors (see Section 10.10.2), baseline eGFR, baseline eGFR by time, and treatment by time interaction terms. The Kenward-Roger option will be used to estimate denominator degrees of freedom and standard errors. ● The above three models will be run using: 
 ○ On- and off-treatment eGFR; ○ On-treatment eGFR values only; ○ On-treatment eGFR values only with subjects who had baseline eGFR ≥ 15ml/min/1.73m²
Model Results Presentation

 ● eGFR observed and change from baseline will be summarized using mean, standard deviation, minimum, P25, median, P75, and maximum at each visit by treatment group. Summaries of on- and off- treatment eGFR, and on-treatment eGFR only will be produced.

Secondary Safety Statistical Analyses: eGFR	

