10.5.2. Baseline Definition & Derivations

10.5.2.1. Baseline Definitions

For all endpoints (except as noted) the baseline value will be the latest non-missing pre-dose assessment on or before the randomization date. This is generally expected to be the pre-dose value from the Day 1 visit, although such values may be missing.

Parameter	Study Assessments Considered As Baseline			Baseline Used in Data Display
	Screen Week -8	Run-in Week -4	Day 1 (Pre-Dose)	
Efficacy				
Hgb			X	Randomization Date
Iron parameters			X	Randomization Date
Safety				
BP parameters, HR and weight ¹			X	Randomization Date
Lipid parameters, renal function parameters, clinical chemistry, hematology, other laboratory and hepatobiliary (liver) tests			X	Randomization Date

Parameter	Study Assessments Considered As Baseline			Baseline Used in Data Display
	Screen Week -8	Run-in Week -4	Day 1 (Pre-Dose)	
PRO				
SF-36 domain and component scores			X	Randomization Date
EQ-5D-5L & VAS			X	Randomization Date
PGI-S			X	Randomization Date
CKD-AQ			X	Randomization Date
WPAI-ANS-CPV			X	Randomization Date

[1]: For subjects who start dialysis during the study, the baseline vital sign values will be used as baseline values for pre- and post- dialysis vital sign displays and baseline weight will be used as the baseline dry weight value.

NOTES:

- Unless otherwise stated, the mean of replicate assessments at any given time point will be used as the value for that time point.

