10.11.1.2. Final Analyses

The multiplicity strategy for this trial will use a combination of a gatekeeper approach on the co-primary endpoints, followed by a closed-test multiplicity procedure wrapped around the family of principal secondary analyses.

[Figure 1](#) illustrates the structure of the statistical testing plan. First, the co-primary endpoints will be evaluated for at least non-inferiority by comparing each two-sided 95% CI to the appropriate non-inferiority margin. Then, the principal secondary analyses will be performed, and superiority will be tested for the individual analyses. Conditional on both co-primary endpoints achieving non-inferiority (i.e., passing the gatekeeper), the family of principal secondary analyses will be formally tested for superiority using the widely known Holm-Bonferroni procedure [[Holm, 1979](#)]. The procedure will be conducted based on a family-wise Type I error rate set at the one-sided 2.5% level.

Figure 1 Multiplicity controlled statistical testing plan**Details of the Holm-Bonferroni procedure for testing secondary endpoints:**

The procedure starts with conducting the statistical analyses for each of the principal secondary analyses and ranking the resulting one-sided p-values from most significant (i.e. the lowest p-value) to the least significant. The Holm-Bonferroni formula is calculated for each rank using a target alpha. The formula for the Holm-Bonferroni method is:

[figure not shown]
$$\text{Holm - Bonferroni}_i = \frac{\text{Target } \alpha}{n - \text{rank}_i + 1}$$

Where:

- the *target α* is the overall alpha level (one-sided 2.5% significance)
- *n* is the total number of tests

The most significant p-value is compared to the rank-associated alpha derived from the Holm-Bonferroni method. If a positive statistically significant treatment effect is observed, then the testing continues to the next ranked test. If the endpoint fails to achieve statistical significance when compared to the Holm-Bonferroni rank-associated alpha, the testing stops and all subsequent endpoints are declared to have failed to achieve statistical significance. This algorithm is described in detail in [Figure 2](#) for the four principal secondary analyses defined for the trial.

Figure 2 The Holm-Bonferroni Procedure for Multiplicity Control

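### The Holm-tested Fine-Gray model for CKD progression leaves out baseline eGFR; the test stays valid, but adding the covariate would be a nearly free gain in efficiency

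*SAP*

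**What the plan says.** SAP Section 8.2.1.2 (CKD Progression) analyses time to progression with a Fine-Gray subdistribution hazards model, "adjusting for the same factors as the co-primary MACE analysis (Section 7.2.2) for the evaluation of superiority". A Cox model with the same terms is supportive. The analysis of unconfirmed eGFR decline repeats the Fine-Gray model, and the component analyses in Section 8.2.2.2 use the same model as the principal analysis.

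The factors are listed in Section 7.2.2: "The Cox Proportional Hazards model will adjust for the following baseline categorical values", followed by treatment, current ESA use and region. eGFR is not among them.

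Baseline eGFR is available. Section 10.5.2.1 gives a Day 1 pre-dose baseline to "Lipid parameters, renal function parameters, clinical chemistry, hematology, other laboratory and hepatobiliary (liver) tests". The SAP uses it as a covariate elsewhere. The eGFR MMRM and slope models in Section 8.2.2.2 contain "baseline eGFR, baseline eGFR by time, and treatment by time interaction terms", and the supportive expanded-covariate MACE model in Section 7.2.2 contains "Continuous variables: baseline Hgb, baseline Age, baseline eGFR, logarithm of baseline UACR, baseline albumin".

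In the CKD-progression analyses, baseline eGFR acts in two places. The analysis set "will be restricted to the subset of subjects with baseline eGFR" of at least 15 mL/min/1.73m². In addition, Section 10.10.1 plans subgroup models by baseline CKD stage for the principal secondary endpoints, and Section 8.2.1.2 says these are Cox models.

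Section 10.11.1.2 tests the four principal secondary analyses by Holm, with a "family-wise Type I error rate set at the one-sided 2.5% level".

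**The concern.** The covariate set was carried over from a cardiovascular endpoint to a renal one. Baseline eGFR is the denominator of the 40% decline and the starting point from which a subject approaches dialysis. The restriction to 15 and above narrows its spread but still leaves CKD stages 2 to 4 in the set.

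Leaving a prognostic covariate out of a hazards model has two consequences when treatment has an effect. The treatment hazard ratio moves toward 1 relative to the covariate-conditional value, and the test loses power. CKD progression is formally tested, and its threshold can be as low as 0.025/4 = 0.00625 one-sided, so a few points of power could matter. The SAP plans a covariate-rich supportive analysis for MACE but none for CKD progression, the endpoint that eGFR bears on most directly.

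**Working it through.** **Figure to reproduce.** There is none. The SAP gives no event count, effect size or power for CKD progression; the 664 events belong to MACE.

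**Inputs from the SAP.** Planned factors: treatment, ESA use, region (7.2.2, 8.2.1.2). Allocation 1:1 (Section 1). Holm thresholds 0.025/(4 − rank + 1) = 0.00625, 0.00833, 0.0125 and 0.025 (10.11.1.2).

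**Assumed inputs, not in the SAP.** N = 3,200 with eGFR of at least 15. Follow-up uniform from 1.0 to 3.5 years. Progression hazard about 0.13 per year and death hazard about 0.06 per year, the latter with a hazard ratio of 1.2 per SD lower eGFR. Hazard ratio g for progression per SD lower eGFR of 1.2, 1.5, 2.0 or 2.5. Treatment hazard ratio HR of 0.80, 0.85 or 1.00.

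**Method.** With x the standardised, sign-reversed eGFR (standard normal) and a the arm:

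- progression hazard = 0.13 · exp(x·ln g − (ln g)²/2) · HR^a
- death hazard = 0.06 · exp(x·ln 1.2)

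Subjects who die stay in the risk set until their own administrative censoring time. This gives the Fine-Gray analysis under administrative censoring only. Each of 600 data sets per scenario was fitted with a alone and with a and x, and superiority was declared when estimate/SE < −z(1−α). Region and ESA use were left out of both fits.

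**Results, without → with baseline eGFR.**

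| HR | g per SD | Mean events | Subdistribution HR | Power at 0.025 | Change (points) | Power at 0.00625 |
|---|---|---|---|---|---|---|
| 0.80 | 1.2 | 675 | 0.804 → 0.803 | 80.8% → 80.7% | −0.1 | 65.7% → 64.7% |
| 0.80 | 1.5 | 665 | 0.807 → 0.803 | 77.8% → 81.0% | 3.2 | 59.8% → 62.7% |
| 0.80 | 2.0 | 636 | 0.811 → 0.801 | 75.5% → 80.3% | 4.8 | 54.7% → 60.3% |
| 0.80 | 2.5 | 600 | 0.823 → 0.806 | 66.8% → 75.2% | 8.4 | 45.7% → 55.7% |
| 0.85 | 1.2 | 694 | 0.849 → 0.849 | 56.3% → 56.7% | 0.4 | 36.2% → 35.8% |
| 0.85 | 1.5 | 679 | 0.851 → 0.848 | 54.2% → 57.7% | 3.5 | 33.7% → 36.5% |
| 0.85 | 2.0 | 650 | 0.858 → 0.850 | 47.2% → 52.7% | 5.5 | 26.2% → 31.0% |
| 0.85 | 2.5 | 613 | 0.867 → 0.853 | 39.5% → 48.5% | 9.0 | 21.8% → 29.3% |

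Monte Carlo SE of a single power figure is at most √(0.5·0.5/600) = 2.0 points.

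**Type I error (HR = 1.00).** Rejection at 0.025 was 2.2% to 2.8% without eGFR and 1.8% to 3.5% with it. The Monte Carlo SE is √(0.025·0.975/600) = 0.6 points, so both agree with the nominal level.

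**Second calculation.** This one fixes adjusted power at 80% and uses the same kind of risk set, with HR 0.85 and 13% to 31% of subjects having events. At one-sided 0.025 the loss is 0 to 2 points for a linear-predictor SD of 0.3 to 0.4 (hazard ratio e^0.3 = 1.35 to e^0.4 = 1.49 per SD), 2 to 4 for SD 0.5 (e^0.5 = 1.65) and 4 to 7 for SD 0.74 (e^0.74 = 2.10).

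Together the two calculations give about 0 to 4 points at 1.2 to 1.5 per SD and about 4 to 9 points at 2.0 to 2.5 per SD.

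**The case against.** The planned choice can be defended. All four Holm members share one covariate set, made up of the stratification factors, and Section 10.10.2 gives the reason: analyse as randomised. The primary MACE model also omits eGFR, which appears for MACE only in a supportive analysis. In the MMRM and slope models it is the usual baseline term for a continuous outcome. The SAP is therefore not inconsistent with itself.

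The prognostic strength is also uncertain. The 40% decline is relative to each subject's own baseline, and the set is truncated at 15, so eGFR may predict the composite less well than it predicts dialysis alone. These points stand. They make the lower end of the range plausible, but they show no harm from adding the term.

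A reader might infer more than the document supports:

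- **That the planned hazard ratio is biased.** It is not. Hazard ratios are non-collapsible, so the planned one estimates a less conditional effect and the adjusted one a more conditional effect.
- **That chance imbalance in eGFR invalidates the test.** Under randomisation the interval and p-value already allow for it.
- **That eGFR enters no CKD-progression model.** The Cox subgroup models by CKD stage contain it as categories, although they are not the Holm test.
- **That 6 to 12 points of power are lost at about 2.1 per SD.** A Cox model with deaths censored gives that figure, but the tested model is Fine-Gray, where the loss at that strength is about 4 to 7 points.

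**Conclusion.** The point holds as a missed efficiency gain, not as an error. The confirmatory model for CKD progression omits a baseline measurement that is already collected and is integral to the endpoint.

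With a real treatment effect, the omission moves the subdistribution hazard ratio toward 1 by at most 0.004 at 1.2 to 1.5 per SD and by 0.008 to 0.017 at 2.0 to 2.5 per SD. The power cost at one-sided 0.025 is about 0 to 4 and about 4 to 9 points respectively. At the strictest Holm step it is no more than about 3 points at 1.2 to 1.5 per SD, and about 5 to 10 points at 2.0 to 2.5.

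All of this depends on the assumed event rates, follow-up, treatment effect and, above all, prognostic strength. If eGFR is only weakly prognostic, or if treatment has no effect, practically nothing is lost.

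**What to change.** Before unblinding, amend SAP Section 8.2.1.2 so that the Fine-Gray model for CKD progression contains continuous baseline eGFR besides treatment, current ESA use and region. Carry the term into the supportive Cox model, the unconfirmed-decline analysis and the component analyses. Keep the model with stratification factors only as a sensitivity analysis. In the subgroup analysis by baseline CKD stage, drop the continuous term, as Section 10.10.1 already does for baseline Hgb groups.

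Log baseline UACR may be added in the same way, with missing values handled by the rule in the expanded-covariate analysis of Section 7.2.2. Its contribution was not quantified here. Baseline eGFR needs no such rule, because membership of the analysis set requires a value.

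The cost is a wording change and one model term, or two with UACR. Both variables are already needed for the expanded MACE model. If the sponsor prefers to leave the tested model alone, the smaller step is a supportive eGFR-adjusted analysis like the one planned for MACE. That would show the conditional estimate but would not recover power for the formal test.

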8.2.2. Additional Secondary Safety Analyses

8.2.2.1. Overview of Planned Additional Secondary Safety Analyses

Table 8 provides an overview of the planned additional secondary safety analyses.

Table 8 Overview of Planned Additional Secondary Safety Analyses

Endpoint	Analysis Population	Absolute								Change from Baseline							
		Stats Analysis			Summary		Individual			Stats Analysis			Summary		Individual		
		T	F	L	T	F	F	L	F	L	T	F	L	T	F	F	L
Additional CV Safety Endpoints¹																	
All-cause mortality	ITT	Y	Y		Y			Y									
CV mortality	ITT	Y	Y		Y												
MI (non-fatal and fatal)	ITT	Y	Y		Y												
Stroke (non-fatal and fatal)	ITT	Y	Y		Y												
MACE or hospitalization for HF (recurrent events)	ITT	Y			Y												
CV mortality or non-fatal MI	ITT	Y	Y		Y												
All-cause hospitalization	ITT	Y	Y		Y												
All-cause hospital re-admission within 30 days	ITT	Y	Y		Y												
MACE or hospitalization for HF or thrombo-embolic events	ITT	Y	Y		Y												
Hospitalization for HF	ITT	Y	Y		Y												
Thromboembolic events	ITT	Y	Y		Y												
Individual components of progression of CKD	ITT	Y	Y		Y												
Blood Pressure																	
SBP, DBP and MAP changes from Baseline ^{2,3}	ITT				Y	Y			Y				Y	Y			
Number of BP exacerbation	ITT	Y			Y												

Endpoint	Analysis Population	Absolute						Change from Baseline							
		Stats Analysis			Summary		Individual		Stats Analysis			Summary		Individual	
		T	F	L	T	F	F	L	T	F	L	T	F	F	L
events per 100 patient years ³															
Patients experiencing at least one BP exacerbation event during study ³	ITT	Y			Y										
Renal Function - eGFR															
eGFR observed and CFB ^{2,3}	ITT	Y			Y				Y			Y	Y		
By Subgroup ^{2,3,4}	ITT	Y			Y				Y			Y	Y		
Rate of decline in eGFR ^{2,3}	ITT	Y			Y										
By subgroup ^{2,3,4}	ITT	Y			Y										

NOTES:

- T = Table, F = Figure, L = Listing, Y = Yes display generated.
- Stats Analysis = Represents TFL related to any formal statistical analyses (i.e. modelling) conducted.
- Summary = Represents TFL related to any summaries (i.e. descriptive statistics) of the observed raw data.
- Individual = Represents FL related to any displays of individual subject observed raw data.

^[1] Adjudicated events used where available.

^[2] Analysis will be performed using all available (on and off treatment) values.

^[3] Analysis will be performed using on-treatment values only.

^[4] Subgroup analysis will only use the ADPKD subgroups defined in Section 10.10.1.

8.2.2.2. Planned Additional Secondary Safety Statistical Analyses

Additional CV Safety Endpoints

Secondary Safety Statistical Analyses: Additional CV Safety Endpoints
Endpoint(s)

 • All-cause mortality, CV mortality, fatal or non-fatal MI, fatal or non-fatal stroke • MACE or hospitalization for HF (recurrent events analysis) • CV mortality or non-fatal MI • All-cause hospitalization (see Section 10.6.4) • All-cause hospital re-admission within 30 days (see Section 10.6.4) • MACE or hospitalization for HF or thromboembolic events • Hospitalization for HF • Thromboembolic events • Individual components of progression of CKD
Model Specification

 • Analysis of the endpoints above (except the recurrent event analysis and components of progression of CKD) will be performed individually using an analysis model identical to that described for the co-primary MACE analysis for the evaluation of superiority, using the event dates defined in Section 10.6.4. Additionally, supportive summaries and analyses for the following endpoints will be generated including fatal events which are identified only through the death endpoint page and do not have a corresponding positively adjudicated endpoint event (see Section 10.6.4): 
 ○ MI ○ Stroke ○ Thromboembolic events: Pulmonary Embolism • For purposes of time-to-event models, subjects who have never been hospitalized will be right-censored (i.e., are still considered to be at-risk) for an all-cause hospital re-admission within 30 days. • The recurrent event analysis of MACE or hospitalization for HF events will use the Prentice, Williams, Peterson (PWP) model [Prentice, 1981], based on the Cox proportional hazards model, to analyze the multiple event data. This model analyzes the time to first, second, etc. events while accounting for the correlation of events within an individual subject. Subjects are at risk for a k^{th} event only if they survived a $(k-1)^{\text{st}}$ event. For the models described below, if there are not at least 15 k^{th} events per arm, the treatment effect associated with the k^{th}, $(k+1)^{\text{th}}$, etc. events will not be estimated. All event times will be relative to randomization, as opposed to intra-event time (i.e. total times rather than gap times will be used). 
Three models will be used. The first model will estimate a common treatment effect, regardless of the number of events experienced by subjects. A second model will be run that allows the treatment effects to differ depending on the number of events experienced by subjects. A third model will be run that allows the treatment effect associated with the time to 1st MACE or hospitalization for HF to differ from a common treatment effect estimated for time to 2nd, 3rd, 4th, etc. MACE or hospitalization for HF. The common treatment effect associated with the time to 2nd, 3rd, 4th, etc. in the third model would provide support for a treatment effect on time to subsequent MACE or hospitalization for HF.
 
It is possible for a patient to die in conjunction with experiencing a series of events in a short


Secondary Safety Statistical Analyses: Additional CV Safety Endpoints

time frame. Ultimately, the CEC will identify the primary cause of death. For the purposes of analysis of time to first and subsequent MACE or hospitalization for HF, only those events occurring prior to and including the ‘fatal’ event will be included. For example, suppose a subject has an MI, followed by a stroke, and dies within a short time frame. If the CEC attributes the death to the MI, only the MI will be used in the analysis. If the CEC attributes the death to the stroke, both the MI and stroke would be used. If the CEC attributes the death to some cause other than the MI and stroke, all three events would be used.

- The three components of CKD progression are: confirmed 40% eGFR decline, chronic dialysis (which includes positively adjudicated cases of dialysis < 90 days and failure to initiate dialysis when indicated), and kidney transplant. Analysis of the individual components of progression of CKD will be performed individually using an analysis model identical to that described for the principal secondary CKD progression analysis for the evaluation of superiority, using the event dates defined in Section 10.6.4.
- Analyses will include only those safety endpoints occurring within the time period for follow-up of CV endpoints, with the exception of all-cause mortality, which will use the time period for vital status (see Section 10.6.4).
- For those endpoints or components of endpoints intended to go through the adjudication process, only the adjudicated results will be used.

Model Checking & Diagnostics

- Refer to [Appendix 12: Model Checking and Diagnostics for Statistical Analyses](#).

Model Results Presentation

- The summary displays of time-to-event endpoints will include a summary of the number and percentage of subjects having events. Summaries of composite endpoints will include the number and percentage of the type of first occurrence by treatment group.
- A summary of all time-to-event endpoints including the number and percentage of subjects and number of events (including first and subsequent events) by type of event will be provided by treatment group.
- Summaries of adjudication details of all-cause mortality will include the number and percentage of subjects by cause of death.
- Summaries of adjudication details of MI will include the number and percentage of events by outcome of MI (fatal or non-fatal), type of MI, increased cardiac markers (y/n), ST segment classification [ST-elevation myocardial infarction (STEMI), non-ST-elevation myocardial infarction (NSTEMI), ECG not interpretable, ECG not available], and Q wave classification (Q wave MI, Non Q wave MI, ECG not interpretable, ECG not available).
- Summaries of adjudication details of stroke will include the number and percentage of events by outcome of stroke (fatal or non-fatal), type of stroke (ischemic, hemorrhagic, or undetermined) and ischemic details (with/without hemorrhagic transformation) and location if hemorrhagic (intraparenchymal, intraventricular, subarachnoid, retinal, unknown location).
- Summaries of adjudication details of heart failure will include the number of events by type: hospitalization for heart failure, heart failure requiring urgent ER/ED visit, heart failure requiring urgent office/practice visit, and fatal heart failure events identified by cause of death only.
- Summaries of adjudication details of thromboembolic events will include the number and percentage of events by type of thromboembolic event (DVT, PE, VAT).
 - Summaries of PEs will include outcome of PE (fatal or non-fatal).
 - Summaries of VATs will include type of VAT (AV fistula, AV graft, central venous catheter, other), method of diagnosis (ultrasound/Doppler, AV imaging, CVC

Secondary Safety Statistical Analyses: Additional CV Safety Endpoints

imaging, other), and treatment (thrombolytic therapy, thrombectomy, angioplasty, stent, surgical intervention, not specified).
 
 • The model results presentation for the endpoints above (except the recurrent event analysis) will be identical to the co-primary MACE model results, with the single exception being the one-sided p-value presented will be for the test of superiority of daprodustat vs. darbepoetin alfa. • For the recurrent events analysis, hazard ratios, two-sided 95% CIs and one-sided chi-squared p-values associated with treatment effects (daprodustat vs. darbepoetin alfa) will be presented for the three models described above. • Summaries that partition the investigator-reported events as (adjudicated to the same event, adjudicated to a different event, adjudicated as a non-event) will be presented. Summaries of investigator/adjudicator agreement by type of event reported by investigators may also be reported. • A summary of all-cause hospitalization will be provided by treatment group including summaries of the number of hospitalizations per subject, average length of stay per hospitalization and primary diagnosis at discharge by system organ class and lower level term. • A summary of all-cause hospital re-admission within 30 days will be provided by treatment group including summaries of the number of re-admissions within 30 days per subject and the primary diagnosis at re-admission discharge by system organ class and lower level term. • A listing of all all-cause mortality events that occur during the study will be provided. This listing will include treatment, site ID, unique subject ID, select demographic information, event date, study day, and cause of death.
Model Results Interpretation

 • One-sided p-values will be compared to 0.025 to assess nominal significance.

Blood Pressure

Secondary Safety Statistical Analyses: Blood Pressure
Endpoint(s)

 • Change from baseline in SBP, DBP and MAP at Week 52 and at end of treatment • Number of BP exacerbation events per 100 patient years • N (%) of subjects with at least one BP exacerbation event during study
Model Specification

 • The difference in change from baseline in BP (SBP, DBP, and MAP) at Week 52 will be analyzed with a mixed model repeated measures (MMRM) approach with an unstructured covariance matrix to compare the difference in means between arms. The models will be fitted to scheduled BP data collected after baseline up to Week 52. Models will be run two times: 
 ○ On-treatment BP values only, excluding values collected during the stabilization period (Randomization date + 1 day to <Week 28). ○ On-treatment BP values only, including values collected during the stabilization period. 
The models will include factors for treatment, time, prognostic randomization stratification factors (see Section 10.10.2), baseline BP parameter and the baseline BP parameter by time and treatment by time interaction terms. Analyses will be done with the MIXED procedure in SAS, using the Kenward-Roger option to estimate denominator degrees of freedom and standard errors. For analyses using on- and off-treatment values, subjects who withdraw from the study before Week 52 are considered to be missing at random and in the analysis using

Secondary Safety Statistical Analyses: Blood Pressure

on-treatment values only, subjects who permanently discontinue randomized treatment before Week 52 are assumed to be missing at random.

- The difference in change from baseline in BP (SBP, DBP, and MAP) at the derived end of treatment (see Section 10.6.4) will be analyzed with an ANCOVA model including terms for treatment, prognostic randomization stratification factors (see Section 10.10.2) and the corresponding baseline BP parameter. This analysis will be performed using on-treatment BP values only.
- The number of on-treatment BP exacerbation events per 100 patient years will be calculated (see Section 10.6.4). Confidence intervals for the rate per 100 patient years will also be reported. For within group rates and the ratio of model estimated exacerbation rates, the point estimates, two-sided 95% confidence intervals, and one-sided p-value for the treatment group comparison will be obtained using a negative binomial model with treatment and the prognostic randomization strata as covariates and the logarithm of time on-treatment as an offset variable.

Model Results Presentation

- BP parameter values (SBP, DBP, and MAP) will be summarized using mean, standard deviation, minimum, P25, median, P75, and maximum at each visit by treatment group. In addition to scheduled visits, the derived baseline value and derived end of treatment values will be summarized (see Section 10.6.4). Summaries of on-treatment BP values only and on- and off-treatment BP values together will be produced. On-treatment BP parameter values will be plotted by visit using a line plot.
- BP parameter change from baseline values (SBP, DBP, and MAP) will be summarized using mean, standard deviation, minimum, P25, median, P75, and maximum at each post-baseline visit by treatment group. In addition to scheduled visits, the derived end of treatment values will be summarized (see Section 10.6.4). Summaries of on-treatment BP values only and on- and off-treatment BP values together will be produced. On-treatment BP parameter change from baseline values will be plotted by visit using a line plot.
- For the MMRM analyses of change from baseline in BP parameters to Week 52, an LSMEANS statement will provide adjusted treatment group means and standard errors and a point estimate and two-sided 95% confidence interval for the adjusted mean treatment difference (daprodustat – darbepoetin alfa) and a one-sided superiority p-value for this test.
- For the ANCOVA analyses of change from baseline in BP parameters to the derived end of treatment, the adjusted mean estimates and standard errors by treatment group, adjusted mean difference, two-sided 95% CI and one-sided superiority p-value for the difference in BP parameter between the daprodustat and darbepoetin alfa arms from the ANCOVA model will be presented. The number of subjects contributing to the analysis and the associated mean and standard deviation of the baseline and end of treatment values will also be displayed with the results of the ANCOVA model.
- The model estimated on-treatment BP exacerbation rates per 100 patient years and associated 95% confidence intervals will be provided by treatment group. The ratio of model estimated on-treatment BP exacerbation rates and associated two-sided 95% confidence interval and one-sided p-value will also be provided for the comparison of daprodustat vs. darbepoetin alfa.
- On-treatment BP exacerbations will be summarized as follows: The number and percent of subjects with 0, 1, 2, 3, 4, 5 and >5 on-treatment BP exacerbations will be provided by treatment group. Additionally, the number and percent of subjects with on-treatment BP exacerbations and number of on-treatment BP exacerbation events will be provided by treatment group, in total and by BP exacerbation type (see Section 10.6.4). The total treatment

Secondary Safety Statistical Analyses: Blood Pressure

exposure in years and overall on-treatment BP exacerbation rate per 100 PY will be provided by treatment group.
 
 ○ The BP exacerbation summary above will be repeated for the following groups and BP values: 
 ▪ All subjects, on-treatment post-dialysis BP values only ▪ All subjects, on-treatment pre-dialysis BP values only
Model Results Interpretation

 ● One-sided p-values will be compared to 0.025 to assess nominal significance.

Renal Function

Secondary Safety Statistical Analyses: eGFR
Endpoint(s)

 ● Change from baseline in eGFR up to week 52 ● Rate of decline in eGFR (eGFR slope)
Model Specification

 ● The difference in change from baseline in eGFR at Week 52 will be analyzed with a mixed model repeated measures (MMRM) approach with an unstructured covariance matrix to compare the difference in means between arms. The models will be fitted to scheduled eGFR data collected after baseline up to Week 52. The models will include treatment, time, prognostic randomization stratification factors (see Section 10.10.2), baseline eGFR, baseline eGFR by time, and treatment by time interaction terms. Analyses will be done with the MIXED procedure in SAS, using the Kenward-Roger option to estimate denominator degrees of freedom and standard errors. ● For the summary table of rate of decline, each subject's actual time since randomization will be used, rather than assigning visit as a categorical variable. For each individual subject in the ITT Population, eGFR will be regressed on time (as a continuous variable), to estimate a slope for each subject. The baseline value of eGFR will be the first value used in the regression. The individual regression slopes will be expressed in ml/min/1.72m² per year. ● For the analysis of rate of decline, the mean slope for eGFR during the study will be estimated by a linear mixed model with random intercept and time to account for between-subject variability. The models will be fitted to scheduled eGFR data collected after baseline, and will include treatment, time, prognostic randomization stratification factors (see Section 10.10.2), baseline eGFR, baseline eGFR by time, and treatment by time interaction terms. The Kenward-Roger option will be used to estimate denominator degrees of freedom and standard errors. ● The above three models will be run using: 
 ○ On- and off-treatment eGFR; ○ On-treatment eGFR values only; ○ On-treatment eGFR values only with subjects who had baseline eGFR ≥ 15ml/min/1.73m²
Model Results Presentation

 ● eGFR observed and change from baseline will be summarized using mean, standard deviation, minimum, P25, median, P75, and maximum at each visit by treatment group. Summaries of on- and off- treatment eGFR, and on-treatment eGFR only will be produced.

Secondary Safety Statistical Analyses: eGFR	
